**RESTRICTED**

	SPONSOR: Scandinavian Biopharma Holding AM (SBH)	PROTOCOL NUMBER: OEV-131	PROTOCOL TITLE: Pre-Study of wild type Enterotoxigenic E.coli (ETEC) Strain for Verification of a planned Challenge Dose	VERSION NO: 1.0
				VERSION DATE: 14JUN2024

**RESTRICTED**

	SPONSOR: Scandinavian Biopharma Holding AM (SBH)	PROTOCOL NUMBER: OEV-131	PROTOCOL TITLE: Pre-Study of wild type Enterotoxigenic E.coli (ETEC) Strain for Verification of a planned Challenge Dose	VERSION NO: 1.0
				VERSION DATE: 14JUN2024

## 14.1 Description of Study Subjects

### 14.1.1 Screen Failures

**Table 7: Summary of Screen Failures**

Inclusion/Exclusion Category	Inclusion/Exclusion Criterion	n a	% b
All Screened Subjects (N=X)	Total number of subjects who failed any eligibility criterion or were eligible but not enrolled	x	xx
Subjects who failed to meet Inclusion Criteria (N=X)	[inclusion criterion 1]	x	xx
	[inclusion criterion 2]	x	xx
	[inclusion criterion 3]	x	xx
Subjects who met Exclusion Criteria (N=X)	[exclusion criterion 1]	x	xx
	[exclusion criterion 2]	x	xx
	[exclusion criterion 3]	x	xx
Subjects who were Eligible but Not Enrolled (N=X)	Alternate subject	x	xx
	Time commitment	x	xx
	Concern of potential risks	x	xx
	Number of procedures/blood draws	x	xx
	Unable to contact subject	x	xx
	COVID-19 pandemic	x	xx
	Other	x	xx

Note: N = Number of subjects belonging to the corresponding inclusion/exclusion category; n = Number of subjects who met the corresponding inclusion/exclusion criterion.

a More than one criterion may be marked per subject.

b Denominator for percentages is the total number of subjects in the corresponding category (N).

**RESTRICTED**

	SPONSOR: Scandinavian Biopharma Holding AM (SBH)	PROTOCOL NUMBER: OEV-131	PROTOCOL TITLE: Pre-Study of wild type Enterotoxigenic E.coli (ETEC) Strain for Verification of a planned Challenge Dose	VERSION NO: 1.0
				VERSION DATE: 14JUN2024

#### 14.1.2 Demographic Data

**Table 8: Summary of Categorical Demographic and Baseline Characteristics - All Enrolled Subjects\***

Variable	Characteristic	All Subjects (N=X)	
		n	%
Sex	Male	x	xx
	Female		
	Intersex		
	Not Reported		
Gender	Cisgender Man	x	xx
	Cisgender Woman		
	Genderqueer		
	Gender Non-binary		
	Gender Non-conforming		
	Transgender Man/ Trans Man		
	Transgender Woman/ Trans Woman		
	Other		
	Not Reported		
Ethnicity	Not Hispanic or Latino	x	xx
	Hispanic or Latino		
	Not Reported		
	Unknown		
Race	American Indian or Alaska Native	x	xx
	Asian		
	Native Hawaiian or Other Pacific Islander		
	Black or African American		
	White		
	Multi-Racial		
	Unknown		
	Not Reported		
Note: N = Number of enrolled subjects; n = Number of enrolled subjects who identify with the corresponding demographic information.			

**RESTRICTED**

	SPONSOR: Scandinavian Biopharma Holding AM (SBH)	PROTOCOL NUMBER: OEV-131	PROTOCOL TITLE: Pre-Study of wild type Enterotoxigenic E.coli (ETEC) Strain for Verification of a planned Challenge Dose	VERSION NO: 1.0
				VERSION DATE: 14JUN2024

**Table 9: Summary of Continuous Demographic and Baseline Characteristics - All Enrolled Subjects\***

Variable	Statistic	All Subjects (N=X)
Age (years)	Mean	xx.x
	Standard Deviation	xx.x
	Median	xx.x
	Minimum	xx
	Maximum	xx
Height (cm)	Mean	xx.x
	Standard Deviation	xx.x
	Median	xx.x
	Minimum	xx
	Maximum	xx
Weight (kg)	Mean	xx.x
	Standard Deviation	xx.x
	Median	xx.x
	Minimum	xx
	Maximum	xx
BMI (kg/m  )	Mean	xx.x
	Standard Deviation	xx.x
	Median	xx.x
	Minimum	xx
	Maximum	xx

Note: N = Number of enrolled subjects.

**RESTRICTED**

	SPONSOR: Scandinavian Biopharma Holding AM (SBH)	PROTOCOL NUMBER: OEV-131	PROTOCOL TITLE: Pre-Study of wild type Enterotoxigenic E.coli (ETEC) Strain for Verification of a planned Challenge Dose	VERSION NO: 1.0
				VERSION DATE: 14JUN2024

#### 14.1.3 Disposition of Subjects

Table 10: Subject Disposition - All Enrolled Subjects

Subject Disposition	All Subjects (N=X)	
	n	%
Screened	x	--
Enrolled	x	100
Received Challenge	x	xx
Completed Inpatient Period Per Protocol	x	xx
Completed Outpatient Visit (Study Day 29)	x	xx
Completed Follow-up (Study Day 180) a	x	xx
Terminated Early from Study	x	xx

Note: N = Number of enrolled subjects; n = Number of subjects who completed the corresponding study milestone.

a For additional details about subjects who terminated early, refer to Listing 2.

**RESTRICTED**

	SPONSOR: Scandinavian Biopharma Holding AM (SBH)	PROTOCOL NUMBER: OEV-131	PROTOCOL TITLE: Pre-Study of wild type Enterotoxigenic E.coli (ETEC) Strain for Verification of a planned Challenge Dose	VERSION NO: 1.0
				VERSION DATE: 14JUN2024

#### 14.1.4 Protocol Deviations

**Table 11: Distribution of Subject-Specific Protocol Deviations by Category and Type - All Enrolled Subjects**

Category	Deviation Type	All Subjects (N=X)	
		No. of Subjects	No. of Deviations
Eligibility/enrollment	Any type	x	x
	Did not meet inclusion criterion	x	x
	Met exclusion criterion	x	x
	ICF not signed prior to study procedures	x	x
	Other	x	x
Treatment administration schedule	Any type	x	x
	Out of window visit	x	x
	Missed visit/visit not conducted	x	x
	Missed treatment administration	x	x
	Delayed treatment administration	x	x
	Other	x	x
Follow-up visit schedule	Any type	x	x
	Out of window visit	x	x
	Missed visit/visit not conducted	x	x
	Other	x	x
Protocol procedure/assessment	Any type	x	x
	Incorrect version of ICF signed	x	x
	Blood not collected	x	x
	Urine not collected	x	x
	Stool not collected	x	x
	Other specimen not collected	x	x
	Too few aliquots obtained	x	x
	Specimen result not obtained	x	x
	Required procedure not conducted	x	x
	Required procedure done incorrectly	x	x
	Study product temperature excursion	x	x
	Specimen temperature excursion	x	x

**RESTRICTED**

	SPONSOR: Scandinavian Biopharma Holding AM (SBH)	PROTOCOL NUMBER: OEV-131	PROTOCOL TITLE: Pre-Study of wild type Enterotoxigenic E.coli (ETEC) Strain for Verification of a planned Challenge Dose	VERSION NO: 1.0
				VERSION DATE: 14JUN2024

Category	Deviation Type	All Subjects (N=X)	
		No. of Subjects	No. of Deviations
	Other	x	x
Treatment administration	Any type	x	x
	Required procedure done incorrectly	x	x
	Study product temperature excursion	x	x
	Other	x	x

Note: N = Number of enrolled subjects.

**RESTRICTED**

	SPONSOR: Scandinavian Biopharma Holding AM (SBH)	PROTOCOL NUMBER: OEV-131	PROTOCOL TITLE: Pre-Study of wild type Enterotoxigenic E.coli (ETEC) Strain for Verification of a planned Challenge Dose	VERSION NO: 1.0
				VERSION DATE: 14JUN2024

## 14.2 Clinical Data

**Table 12: Number and Percentage of Subjects Meeting the Primary Endpoint and Unadjudicated Primary Endpoint - Full Analysis Set\***

Endpoint Type	All Subjects (N=X)		
	n	%	95% CI a
Primary Endpoint	x	xx	xx.x, xx.x
Unadjudicated Primary Endpoint	x	xx	xx.x, xx.x

Notes: N = Number of subjects in the Full Analysis Set; n = Number of subjects meeting the corresponding endpoint.

a Exact binomial confidence interval calculated via Clopper-Pearson methodology.

**RESTRICTED**

	SPONSOR: Scandinavian Biopharma Holding AM (SBH)	PROTOCOL NUMBER: OEV-131	PROTOCOL TITLE: Pre-Study of wild type Enterotoxigenic E.coli (ETEC) Strain for Verification of a planned Challenge Dose	VERSION NO: 1.0
				VERSION DATE: 14JUN2024

**Table 13: Maximum Diarrhea Severity - Full Analysis Set\***

Variable	Category	All Subjects (N=X)		
		n	%	95% CI b
Maximum Diarrhea Severity a	None	x	xx	-
	Mild	x	xx	-
	Moderate	x	xx	-
	Severe	x	xx	xx.x, xx.x
	Any Diarrhea (Mild-Severe)	x	xx	xx.x, xx.x

Notes: N = Number of subjects in the Full Analysis Set; n = Number of subjects with the corresponding maximum diarrhea severity during the inpatient period.

a Maximum diarrhea severity refers to the maximum severity of any diarrhea episode passed by each subject during the inpatient period.

b Exact binomial confidence interval calculated via Clopper-Pearson methodology.

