Risks Associated with Antibiotics: Therapeutic antibiotics for use in this study are licensed, approved medications that have been used extensively, and shown to be very safe with only rare side effects. The most commonly reported side effects for ciprofloxacin are gastrointestinal symptoms (nausea, vomiting, and diarrhea) in as many as 5 persons in 100. Other reported symptoms in less than 1 person in 100 include rash, dizziness, and headache. Rarely, allergic reactions to these medications have been observed. Ciprofloxacin is not recommended for use in pregnancy due to concerns of joint damage to the unborn child (based on studies in young animals). Pregnancy is exclusionary for study participation and is documented through testing prior to study interventions and provided discussion on methods to prevent pregnancy during study. Fluoroquinolones, including ciprofloxacin, are associated with an increased risk of tendonitis and tendon rupture in all ages. The risk of developing fluoroquinolone-associated tendonitis and tendon rupture is further increased in older patients, usually over 60 years of age, in patients taking corticosteroid drugs, and in patients with kidney, heart, or lung transplants, all of whom are excluded from this study. *Clostridium difficile*-associated diarrhea (CDAD/ pseudomembranous colitis) has been reported with use of nearly all antibacterial agents.

Subjects will not be discharged until they are well and have had at least two consecutive stool cultures negative for the challenge strain. Both stool cultures may be from the same day. Approximately 6 months after challenge, all subjects will have a follow-up contact by telephone to inquire about the occurrence of any new chronic illnesses or serious adverse events.

Risks Associated with SARS-CoV-2 Exposure and Risk Mitigation: The risk that the COVID-19 pandemic will influence the possibility to perform the study according to plan, or influence the results of the study, will be continuously assessed by the study team. Since the subjects are planned to be enrolled in Q1 2024, when a majority of the adult US population will have been vaccinated or infected with SARS-CoV-2, the risk that the pandemic will have major influence on the study is deemed to be small.

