9.5.3.1.3 ETEC Disease Severity

A three-component disease score utilizing objective signs, subjective symptoms and stool output will be analyzed for the entirety of the clinical illness (Table 7). The scoring goes from 0 (no diarrhea and no other signs or symptoms) to the maximum of 8 (severe ETEC disease) [31].

Table 7. Disease Severity Score Components

Parameter	Outcome	Score
Objective signs	>1 episode of vomiting/24 hours OR any fever	2
	1 episode of vomiting AND no fever	1
	No vomiting AND no fever	0
Subjective symptoms	Moderate-severe lightheadedness OR Severe nausea, malaise, headache or abdominal cramps	2
	Mild lightheadedness OR Mild-moderate nausea, malaise, headache or abdominal cramps	1
	No 'subjective symptoms'	0
Diarrhea score	>1000 grams of grade 3-5 stool OR >12 grade 3-5 stools in 24 hours	4
	>600 to \leq 1000 grams of grade 3-5 stool OR >7 to 12 grade 3-5 stools in 24 hours	3
	>400 to \leq 600 grams of grade 3-5 stool OR >4 to \leq 7 grade 3-5 stools in 24 hours	2
	>0 to \leq 400 grams of grade 3-5 stool OR 1 to 4 grade 3-5 stools in 24 hours	1
	No grade 3-5 stools	0

1 gram of grade 3-5 stool is considered equivalent to 1 mL of grade 3-5 stool.

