9.5.6.2.3 Post Challenge phase (Day 2 to 8)

- Daily medical interview (including assessment of ETEC disease-specific solicited events) and focused physical examination
- Vital signs (temperature, pulse and blood pressure) will be measured at least 3 times daily

- All stools will be collected for weighing and grading. Up to 3 stool samples will be sent daily for culture. If a volunteer is unable to provide samples, they will be asked to provide a self-collected rectal swab (up to 3 per day). (If the participant does not produce a stool or enough stool on any day to obtain all samples, this will not be considered a protocol deviation.)
- Record any AEs, AESIs and SAEs
- Changes in concomitant medications will be captured
- Antibiotic treatment will be started on Day 6 (5 days after challenge) or according to criteria for early antibiotic treatment (see Section 9.4.8.2)
- Collect blood samples on Days 3, 4 and 8 for immunogenicity endpoints (exploratory)
- Collect daily fecal samples for immunogenicity endpoints (exploratory)
- Collect ETEC Impact on ADLs survey responses on Day 6

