## 2.6. Clinical Variables

### 2.6.1. Stool Output

Every stool passed during the inpatient period (Day 1 through up to Day 9) will be collected. Clinic staff will grade each stool according to the scale in Section [2.5.1](#) Time of stool (hour and minute), stool weight (grams), and stool grade (Grade 1 through Grade 5) will be recorded and used to determine whether diarrhea occurred according to the definitions in Section [2.5.1](#).

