### 2.6.2. ETEC Disease Severity Score

ETEC disease severity will be assessed according to a three-component disease score consisting of objective signs (vomiting frequency and fever), subjective symptoms (lightheadedness, nausea, malaise, headache, and abdominal cramps), and stool output (maximum number and weight of grade 3-5 stools during a 24-hour period), all measured regularly throughout the entire inpatient period (see [Section 2.3](#) for schedule of events).

See [Table 2](#) for specific ETEC disease severity scoring criteria. Scores may range from 0 (no diarrhea and no other signs or symptoms of ETEC disease) to 8 (severe ETEC disease). One score will be assigned to each subject based on the maximum severity of each scoring component during the inpatient period.

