#### 5.2. Diarrhea Incidence and Severity

[Table 13](#) will display the number and percentage of subjects with diarrhea, with corresponding 95% CIs, by maximum severity and maximum stool grade throughout the 120-hour observation period.

Total number and weight of grade 3-5 stools passed during the 120-hour observation period, as well as maximum number and weight of grade 3-5 stools during a 24-hour window, will be summarized by mean, standard deviation, median, minimum, and maximum in [Table 14](#).

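### SAP Table 13 (any and severe diarrhea) has two conflicting observation windows, and time to diarrhea onset counts events beyond 120 h while censoring event-free subjects at 120 h

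*SAP*

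**What the plan says.** Table numbers here are those in the captions of the SAP mock-ups.

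**Any and severe diarrhea.** SAP section 5.2 says Table 13 will show subjects with diarrhea "by maximum severity and maximum stool grade throughout the 120-hour observation period". The Table 13 mock-up says otherwise in two places. Its note has "n = Number of subjects with the corresponding maximum diarrhea severity during the inpatient period", and footnote a has "Maximum diarrhea severity refers to the maximum severity of any diarrhea episode passed by each subject during the inpatient period". The two windows differ in length: SAP section 2.6.1 states "Every stool passed during the inpatient period (Day 1 through up to Day 9) will be collected". Protocol section 8.2.1 gives a 120-hour window for total stool number and weight, but none for severe diarrhea or diarrhea of any severity.

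**Time to diarrhea onset.** SAP section 2.5.4.3 and Table 15 footnote d count the first episode during the inpatient period. Section 2.5.4.3 censors subjects without an episode at 120 h. Table 15 footnote e censors the same subjects at discharge from the unit.

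**Context.** The primary endpoint (SAP 2.2.1) and its unadjudicated version (SAP 2.5.3) admit only episodes beginning by 120 h. Subjects not treated earlier start antibiotics on the morning of Day 6, five days after challenge (protocol 9.4.8.2 and 9.5.6.2.3). Tables 13 and 15 carry the topline asterisk, and SAP section 8.1 treats topline results as final.

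**The concern.** Section 5.2 and the Table 13 mock-up cannot both be programmed, and the protocol does not decide between them. Under the mock-up, an episode that starts after the planned antibiotics counts as challenge diarrhea in Table 13, without adjudication, although the same episode could not count in Table 12. The inpatient window also differs between subjects, because stool grading normally stops after two negative cultures and discharge depends on the subject's course.

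The onset analysis has a second problem. If events can occur after 120 h but every event-free subject leaves the risk set at 120 h, the only subjects at risk afterwards are those who will have an event. The Kaplan-Meier estimate then breaks down.

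Both tables describe what the planned challenge dose does, and both are read at topline in an open-label study. The window should therefore not be left to be chosen at programming.

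**Working it through.** **1. The plan's own precision figures.** SAP section 2.4.1 gives 95% Clopper-Pearson intervals for N = 25. Recomputed from beta quantiles, 15/25 (60%) gives (0.387, 0.789) and 18/25 (72%) gives (0.506, 0.879). Both agree with the stated (0.39, 0.79) and (0.51, 0.88). The same method is used below.

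**2. What the longer window adds.** Day 1 to Day 9 is 8 days, or 8 × 24 = 192 h. The excess over the observation period is 192 − 120 = 72 h, essentially all after the planned Day 6 antibiotic start (5 × 24 = 120 h). On the first-line drug, protocol section 7.3.2 says: "The most commonly reported side effects for ciprofloxacin are gastrointestinal symptoms (nausea, vomiting, and diarrhea) in as many as 5 persons in 100".

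**3. Effect on the any-diarrhea rate.** One reclassified subject adds 1/25 = 4.0 points or 1/30 = 3.3 points. For illustration, assume 80% have diarrhea by 120 h, the approximate earlier attack rate in protocol section 9.2:

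| N | 120 h window | one late-onset subject added |
|---|---|---|
| 25 | 20/25 = 80% (0.593, 0.932) | 21/25 = 84% (0.639, 0.955) |
| 30 | 24/30 = 80% (0.614, 0.923) | 25/30 = 83.3% (0.653, 0.944) |

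**4. How likely a reclassification is.** Only subjects free of diarrhea at 120 h can move into the any-diarrhea row. At 20% of N that is 5 of 25 or 6 of 30. Take 5% as the chance of late antibiotic-related diarrhea. This is an upper figure, because the protocol's 5 in 100 covers nausea, vomiting and diarrhea together. The range 2–10% is assumed.

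- Expected number: 5 × 0.05 = 0.25 (N = 25); 6 × 0.05 = 0.30 (N = 30).
- Chance of at least one: 1 − 0.95^5 = 0.226; 1 − 0.95^6 = 0.265.
- At 2%: 1 − 0.98^5 = 0.096; 1 − 0.98^6 = 0.114.
- At 10%: 1 − 0.90^5 = 0.410; 1 − 0.90^6 = 0.469.

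For the severe row, anyone not yet severe could move. The documents give no rate from which to estimate that.

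**5. Time to onset.** Illustration: N = 25, 20 onsets by 120 h, one at 140 h, four never. With no censoring before 120 h, the event-free fraction then is 5/25 = 0.20.

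- *Section 2.5.4.3* (four censored at 120 h): one subject is at risk at 140 h, so 0.20 × (1 − 1/1) = 0 and cumulative incidence is 100%.
- *Table 15 footnote e* (four censored at discharge, taken as 192 h): five are at risk, so 0.20 × (1 − 1/5) = 0.16 and incidence is 84%.
- *120 h event window*: incidence stays at 80%.

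The first result is general. With any number of onsets after 120 h and every event-free subject censored at 120 h, the last onset is always the only subject left at risk, so the curve ends at 100%. In this example the quartiles do not change, since 19/25 = 76% is reached before 120 h. The damage is to the tail of the curve and the reported maximum.

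**6. Why the window should be set by onset.** In the example in SAP Listing 6, episode 2 has loose stools at 105 h 55 min and 122 h 3 min, 16 h 8 min apart, totalling 62 g. Taken alone and cut strictly at 120 h, it is one stool and no diarrhea. Under an onset-by-120 h rule it is mild diarrhea. The wording in section 5.2 leaves this open.

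**The case against.** The strongest reply is that little is at stake. The primary endpoint and its unadjudicated version are fixed at onset by 120 h. Listing 6, also a topline output, flags for each episode whether it began before 120 h, so a late episode would be seen. Diarrhea, as a solicited event, also receives an investigator judgement of its relation to challenge, procedures and antibiotics. All of this is correct and limits the size of the problem. It does not resolve it, because neither Table 13 nor Table 15 uses the flag or the causality judgement.

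A reader might infer more than the documents support:

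- **A material upward bias.** Applying 5% to all subjects gives 0.05 × 25 = 1.25 to 0.05 × 30 = 1.5. That counts any gastrointestinal symptom in anyone, including subjects who already have diarrhea. The relevant figure is 0.25–0.30.
- **A conflict in the disease severity score.** SAP 2.6.2 says "One score will be assigned to each subject based on the maximum severity of each scoring component during the inpatient period", while protocol 9.5.3.1.3 says the score "will be analyzed for the entirety of the clinical illness". The protocol wording is not a 120-hour limit, and the SAP can be read as putting it into operation.
- **A fault in all stool endpoints.** Table 14 shows 120-hour and inpatient totals in separately labelled rows.
- **Removal of antibiotic-related diarrhea by a 120 h limit.** Diarrhea after early treatment, before Day 6, falls inside either window. In the two earlier studies reporting it (protocol Table 3), early antibiotics were given to 80% and 50%.

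**Conclusion.** The contradiction is real and lies within the SAP: Table 13 has two windows, and time to onset has two censoring rules. The rule in section 2.5.4.3 is unsound as written once any onset falls after 120 h. In the illustration it gives 100%, against 84% with censoring at discharge and 80% with a 120 h event window.

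For Table 13 the expected numerical effect is small: 4.0 or 3.3 points per reclassified subject, with a 23–26% chance of at least one. This rests on 20% being diarrhea-free at 120 h and on a 5% late rate that leans high. Over the assumed 2–10% range the chance runs from 10% to 41% (N = 25) and from 11% to 47% (N = 30). The Kaplan-Meier figures assume event-free subjects stay to 192 h and would shift if some left earlier.

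The point does not extend to the primary endpoint, the Table 14 totals or the severity score. The correction is worth making because these are topline secondary results and their definition should be fixed in advance.

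**What to change.** Use one window, diarrhea episodes beginning by 120 h post-challenge and followed to resolution, as for the primary endpoint. State it in:

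- SAP section 5.2, replacing the present 120-hour wording;
- the Table 13 note and footnote a;
- section 2.5.4.3 and Table 15 footnote d, for the onset event;
- section 2.5.4.3 and Table 15 footnote e, for censoring: event-free subjects at 120 h or discharge, whichever is first. Footnote e already gives this rule for the primary endpoint.

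If an inpatient-period version is wanted, show it as a separately labelled supplementary row, as Table 14 does.

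The cost is text and footnote edits plus a filter on the episode-start flag already in Listing 6. No new data are needed. The reported rates may be slightly lower. A common window lessens unequal observation but does not remove it, because discharge before 120 h remains possible.

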**RESTRICTED**

	SPONSOR: Scandinavian Biopharma Holding AM (SBH)	PROTOCOL NUMBER: OEV-131	PROTOCOL TITLE: Pre-Study of wild type Enterotoxigenic E.coli (ETEC) Strain for Verification of a planned Challenge Dose	VERSION NO: 1.0
				VERSION DATE: 14JUN2024

**Table 14: Summaries of Number and Weight of Grade 3-5 Stools - Full Analysis Set\***

Variable	Statistic	All Subjects (N=X)
Total Number of Grade 3-5 Stools during 120-Hour Observation Period	Mean	xx.x
	Standard Deviation	xx.x
	Median	xx.x
	Minimum	xx
	Maximum	xx
Total Number of Grade 3-5 Stools during Inpatient Period	Mean	xx.x
	Standard Deviation	xx.x
	Median	xx.x
	Minimum	xx
	Maximum	xx
Total Weight (g) of Grade 3-5 Stools during 120-Hour Observation Period	Mean	xx.x
	Standard Deviation	xx.x
	Median	xx.x
	Minimum	xx
	Maximum	xx
Total Weight (g) of Grade 3-5 Stools during Inpatient Period	Mean	xx.x
	Standard Deviation	xx.x
	Median	xx.x
	Minimum	xx
	Maximum	xx
Maximum Number of Grade 3-5 Stools in 24-Hour Window during 120-Hour Observation Period	Mean	xx.x
	Standard Deviation	xx.x
	Median	xx.x
	Minimum	xx
	Maximum	xx
Maximum Number of Grade 3-5 Stools in 24-Hour Window during Inpatient Period	Mean	xx.x
	Standard Deviation	xx.x
	Median	xx.x
	Minimum	xx
	Maximum	xx

